6.2 Definition of an Adverse Event

An AE is any untoward medical occurrence in an enrolled subject, regardless of its causal relationship to the investigational medicinal product. Only AEs of interest should be collected and reported.

AEs of interest include the following:

- new malignancy
- new incidence or exacerbation of a pre-existing neurologic disorder
- new incidence or exacerbation of a prior rheumatologic or other autoimmune disorder
- unexpected hospitalization

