6.3 Definition of a Serious Adverse Event

An SAE is any untoward medical occurrence in an enrolled subject that results in death; is immediately life-threatening; requires inpatient hospitalization or prolongation of existing hospitalization; results in persistent or significant disability or incapacity; or is a congenital anomaly or birth defect. Only SAEs related to ADVM-043 should be collected and reported.

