6.4 Assessment of Severity

The severity or intensity of an AE refers to the extent to which an AE affects the subject's daily activities. The intensity of the AE will be rated according to the Common Terminology Criteria for Adverse Events (CTCAE) (National Cancer Institute 2017):

- Grade 1: Mild; asymptomatic or mild symptoms; clinical or diagnostic observations only; intervention not indicated.
- Grade 2: Moderate; minimal, local, or noninvasive intervention indicated; limiting age-appropriate instrumental activity of daily living (preparing meals, shopping for groceries or clothes, using the telephone, managing money).
- Grade 3: Severe or medically significant but not immediately life-threatening; hospitalization or prolongation of hospitalization indicated; disabling; limiting self-care activity of daily living (bathing, dressing, and undressing, feeding self, using the toilet, taking medications, and not bedridden).
- Grade 4: Life-threatening consequences; urgent intervention indicated.
- Grade 5: Death related to AE.

Changes in the severity of an AE should be documented to allow an assessment of the duration of the event at each level of severity. AEs characterized as intermittent do not require documentation of onset and duration of each episode.

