6.7 Adverse Event Reporting

The Investigator or designee is to be responsible for collecting all events that meet the definition of AEs of interest (Section 6.2). AEs of interest should be recorded on the CRF by the Investigator or designee

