11.7.1.2 Summary of Adverse Events of Interest by SOC and PT

Number and percentage of subjects will be summarized by cohort, system organ class and preferred terms. Percentages will be based on FAS population. Events will be displayed in the descending order of frequency in “Total”.

The same will be repeated for ADVM-043 related AEs of interest, Serious AEs of interest, ADVM-043 related serious AEs.

Listings for ADVM-043 related AEs of interest, serious AEs of interest will be listed similar to Listing 16.2.7.1 with respective information.

Death due to AEs will also be listed separately.

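### Protocol 6.2 and 6.3 give opposite collection rules for an unrelated serious AE of interest, and for a related SAE outside the four categories

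*Protocol*

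**What the plan says.** Protocol 6.2 starts from a definition that ignores cause: "An AE is any untoward medical occurrence in an enrolled subject, regardless of its causal relationship to the investigational medicinal product". It then limits collection: "Only AEs of interest should be collected and reported". The four categories are new malignancy, neurologic disorder, rheumatologic or other autoimmune disorder, and "unexpected hospitalization". None carries a causality condition. Section 6.7 makes the investigator responsible for all events that meet this definition.

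Protocol 6.3 counts an event as an SAE if, among other criteria, it "requires inpatient hospitalization or prolongation of existing hospitalization". Death, immediate threat to life and lasting disability also qualify. The section ends: "Only SAEs related to ADVM-043 should be collected and reported". Section 6.8 has related SAEs entered on the CRF.

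Protocol 6.5 says that the investigator's view of relationship does not decide whether an event is reported.

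The primary endpoint (Protocol 2.2.1, SAP 7.1) names two groups: AEs of interest, and SAEs related to ADVM-043. SAP 11.7.1.1 has separate rows for serious adverse events (row 4) and ADVM-043 related serious adverse events (row 5). After the main table of AEs of interest, SAP 11.7.1.2 adds: "The same will be repeated for ADVM-043 related AEs of interest, Serious AEs of interest, ADVM-043 related serious AEs". SAP 10.6 repeats the restriction to AEs of interest, and SAP 11.7 says that only these will be summarized.

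**The concern.** The categories in 6.2 and the SAE criteria in 6.3 overlap. An unexpected inpatient admission meets both definitions. So does a new malignancy, neurologic event or autoimmune event that is fatal, life-threatening or disabling, or that leads to admission. If such an event is judged unrelated, 6.2 and 6.7 say to collect it and 6.3 says not to.

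This touches the study's only objective and only endpoint. The study exists to pick up delayed events, and the relationship of a single event to a gene therapy given years earlier is hard to judge. Section 6.5 also sets the threshold for related at a reasonable possibility, and does not accept mere inability to exclude a link. Serious events with a plausible alternative cause will therefore often be called unrelated. An event that is never recorded cannot be reassessed later or compared across the three dose cohorts in SAP 10.2, and SAP 8.1 imputes nothing.

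**Working it through.** The documents state no figure on this point, so there is none to reproduce. The check applies each rule literally to every kind of event. An event is of interest or not, serious or not, and related or not, which gives 2 × 2 × 2 = 8 kinds. The last sentence of 6.3 governs only serious events.

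| Of interest (6.2) | Serious (6.3) | Related | Under 6.2 and 6.7 | Under last sentence of 6.3 | Result |
|---|---|---|---|---|---|
| Yes | No | Yes | Collect | Does not apply | Collected |
| Yes | No | No | Collect | Does not apply | Collected |
| Yes | Yes | Yes | Collect | Collect | Collected |
| Yes | Yes | No | Collect | Leave out | **Conflict** |
| No | Yes | Yes | Leave out | Collect | **Conflict** |
| No | Yes | No | Leave out | Leave out | Not collected |
| No | No | Yes | Leave out | Does not apply | Not collected |
| No | No | No | Leave out | Does not apply | Not collected |

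The rules agree or do not compete for six kinds and contradict each other for two.

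**First conflict: unrelated serious AE of interest.** Section 6.5 points towards collecting it. No passage says that 6.5 or 6.2 overrides 6.3.

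**Second conflict: related SAE outside the four categories.** Sections 6.3 and 6.8 and the endpoint require it. The limiting sentence in 6.2, repeated in SAP 10.6, excludes it.

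**Effect on the SAP tables.** Let R be the number of subjects with at least one related serious event, and U the number whose serious events are all unrelated. The denominator is the FAS.

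- If 6.2 prevails: row 4 = (R + U)/FAS and row 5 = R/FAS. They differ by U/FAS.
- If 6.3 prevails: no unrelated serious event is recorded, so U = 0 and row 4 = row 5 = R/FAS.

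Under the second reading the table of serious AEs of interest in SAP 11.7.1.2 holds only related events. The fatal row in 11.7.1.1 holds only related deaths, although Protocol 6.10 asks for an autopsy after any death on study. Row 1 loses every subject whose only AE of interest was serious and unrelated, while a subject with a non-serious unrelated one stays in.

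This applies to events collected in this study. AEs of interest imported from the treatment study under SAP 10.6 could still make rows 4 and 5 differ.

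**The case against.** The strongest reply is that the documents, read together, show what was meant. The pairing of AEs of interest with related SAEs recurs in the endpoint, in Protocol 3.4, 4.3, 5.2, 6.6 and 6.9, and in the assessment schedule. Section 5.2 has sites record the relationship of each AE of interest, and 6.6 has them record both seriousness and relationship. The SAP separates serious from related serious events. On this reading 6.3 adds related SAEs from outside the four categories and takes nothing away. Sites also work from a study manual and CRF guidelines that are not among the documents.

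This reading is probably the intended one, and it shows which way to settle the conflict. But it has to be inferred. The sentence in 6.3 is categorical and sits in the section that defines an SAE. Even on the intended reading 6.5 is too broad, because relationship does decide whether an SAE outside the four categories is collected.

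A reader might infer three stronger points that the documents do not support:

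- **That every unexpected hospitalization is an SAE.** Section 6.2 does not say inpatient and 6.3 does, so a stay not classed as inpatient may fall outside 6.3.
- **That hospitalized events are Grade 3 or higher by definition, so the severity tables restate the entry rule.** Section 6.4 rates severity by effect on daily activities. The phrase "hospitalization or prolongation of hospitalization indicated" is one of several Grade 3 descriptors, and nothing sets a minimum grade for an admission. SAP 11.7.1.3 already splits severity by system organ class and preferred term, so a separate line for admissions would be a matter of layout.
- **That the plan prescribes dropping the worst unrelated events.** That happens only if a site lets 6.3 override 6.2, 6.5 and 6.7.

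**Conclusion.** The contradiction is in the text and should be removed. Two of the eight kinds of event fall under opposite collection rules, and both belong to the primary endpoint. For the first, the difference between the readings is every unrelated serious AE of interest that arises in this study, which is the whole gap between rows 4 and 5 of SAP 11.7.1.1. For the second, it is every related SAE outside the four categories.

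The size cannot be given as a count or percentage, because the documents contain no sample size and no expected event rates.

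The conclusion rests on three assumptions: at least some unexpected hospitalizations are inpatient admissions; related in 6.3 has the meaning SAP 10.6 gives it for this study (definitely or likely related); and rows 4 and 5 draw on the same set of recorded events. The first matters only for the hospitalization category. The conflict for a fatal or disabling malignancy, neurologic or autoimmune event does not depend on it.

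**What to change.** Reconcile 6.2, 6.3 and 6.5 in line with the endpoint and the SAP tables:

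- **Protocol 6.3, last sentence.** Replace with: *SAEs that are also AEs of interest (Section 6.2) are collected regardless of relationship; SAEs outside the four categories are collected only if related to ADVM-043.*
- **Protocol 6.2, limiting sentence.** Replace with: *Only AEs of interest, and SAEs related to ADVM-043 (Section 6.3), should be collected and reported.*
- **Protocol 6.5.** Confine the statement that relationship does not affect reporting to AEs of interest.
- **Protocol 5.2, SAP 10.6 and SAP 11.7.** Mirror the same rule, so that related SAEs outside the four categories are both collected and summarized.

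The study manual and CRF guidelines should be checked against the new wording. The cost is a few sentences in each document, with no new visits, procedures or tables. If events have already been collected, sites should be asked whether any unrelated serious AE of interest, or any related SAE outside the four categories, was left out.

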6.4 Assessment of Severity

The severity or intensity of an AE refers to the extent to which an AE affects the subject's daily activities. The intensity of the AE will be rated according to the Common Terminology Criteria for Adverse Events (CTCAE) (National Cancer Institute 2017):

- Grade 1: Mild; asymptomatic or mild symptoms; clinical or diagnostic observations only; intervention not indicated.
- Grade 2: Moderate; minimal, local, or noninvasive intervention indicated; limiting age-appropriate instrumental activity of daily living (preparing meals, shopping for groceries or clothes, using the telephone, managing money).
- Grade 3: Severe or medically significant but not immediately life-threatening; hospitalization or prolongation of hospitalization indicated; disabling; limiting self-care activity of daily living (bathing, dressing, and undressing, feeding self, using the toilet, taking medications, and not bedridden).
- Grade 4: Life-threatening consequences; urgent intervention indicated.
- Grade 5: Death related to AE.

Changes in the severity of an AE should be documented to allow an assessment of the duration of the event at each level of severity. AEs characterized as intermittent do not require documentation of onset and duration of each episode.

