2.2 Endpoints

2.2.1 Primary Endpoint

- Type, frequency, severity, duration, and relationship to ADVM-043 of adverse events (AEs) of interest and serious adverse events (SAEs) related to ADVM-043

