10.6 Adverse Events Flags

An AE is any untoward medical occurrence in an enrolled subject, regardless of its causal relationship to the investigational medicinal product.

Only AEs of interest will be collected and reported in the current study. AEs of interest that are continuing from the previous study will be imported for long term follow-up.

AEs of interest include:

- new malignancy
- new incidence or exacerbation of a pre-existing neurologic disorder
- new incidence or exacerbation of a prior rheumatologic or other autoimmune disorder
- unexpected hospitalization

Study Period:

All AEs will be counted once under the below period in which the AE has started.

- Previous Study: Reported from AE (External).
- Screening – Year 1: If AE start date is after screening and on or before Year 1 visit date.
- Year 1 – Year 2: If AE start date is after Year 1 and on or before Year 2 visit date.
- Year 2 – Year 3 (EOS): If AE start date is after Year 2 and on or before Year 3 visit date.

Related Adverse Events:

- AE (External): includes Possibly, Probably and Definitely Related Adverse Events
- AE: includes Definitely and Likely Related Adverse Events.

Relationship to ADVM-043 will be flagged separately.

Severity:

Subjects with the same AE of interest and different severities will be flagged for the most intense severity. i.e., If the same event has been reported twice with severity 'Grade 1 – Mild' and 'Grade 3 – Severe' then the subject will be flagged as 'Grade 3 – Severe'. AEs that are missing severity will be presented in summary tables as 'Grade 3 – Severe'.

Duration of AEs:

Duration of Adverse events (days) will be calculated as follows: (AE End date – AE Start date) + 1.

For adverse events that are ongoing at end of study, date of end of study will be considered as AE End date.

11 Statistical Analyses

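### Undefined waiver of episode dates for intermittent AEs: recurrent flares of an AE of interest can become one event, dated to the first episode, with a duration that includes symptom-free time

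*Protocol*

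**What the plan says.** Protocol 2.2.1 makes the primary endpoint "Type, frequency, severity, duration, and relationship to ADVM-043 of adverse events (AEs) of interest" and of related SAEs; SAP 7.1 repeats it. Frequency and duration are therefore both named components.

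Protocol 6.2 restricts AE collection to four categories of interest. Two of them are "new incidence or exacerbation of a pre-existing neurologic disorder" and "new incidence or exacerbation of a prior rheumatologic or other autoimmune disorder". The others are new malignancy and "unexpected hospitalization". Protocol 6.3 restricts SAE collection to those related to ADVM-043.

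Protocol 6.4 contains two adjacent recording rules. The first is "Changes in the severity of an AE should be documented to allow an assessment of the duration of the event at each level of severity". The second is "AEs characterized as intermittent do not require documentation of onset and duration of each episode". Neither document defines intermittent, and AEs of interest are not exempted.

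SAP 10.6 has two rules that depend on how an event was recorded: "All AEs will be counted once under the below period in which the AE has started", and "Duration of Adverse events (days) will be calculated as follows: (AE End date – AE Start date) + 1". An AE ongoing at end of study takes the end-of-study date as its end date. An AE of interest continuing from the earlier study is imported and assigned to that study's period. The SAP has no rule for intermittent AEs, and SAP 8.1 rules out imputation of missing data.

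**The concern.** In a study that collects all AEs, such a waiver would spare sites from dating each recurrence of a trivial symptom. Here no minor AEs are collected, so the waiver can apply only to events that belong to the primary endpoint. The exacerbation categories are where recurrence is foreseeable.

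If recurrent flares are entered as one intermittent AE, three quantities are affected: the event count (the m that SAP 8 reports beside the subject count n), the study-period flag, and the listed duration. With intermittent undefined, two sites could record the same flare history differently and both comply. Protocol 1.0 justifies the study by the possibility of adverse events delayed by months or years, so the timing of later episodes is relevant. Episode dates that were never documented cannot be recovered at analysis.

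**Working it through.** The plan states no sample size, event rate or flare rate, so there is no figure of its own to reproduce. The check applies the SAP 10.6 rules to assumed flare histories, recorded first per episode and then as one intermittent AE.

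**Rules used (SAP 10.6)**
- Period: the one containing the AE start date, counted once.
- Duration in days: end date − start date + 1.
- Ongoing AE: end date = end-of-study date.

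**Illustration 1: count and duration.** Assume three 5-day flares, the first starting on day 1 and the last resolving on day 365.
- Per episode: 3 events; 3 × 5 = 15 days.
- One intermittent AE: 1 event; (365 − 1) + 1 = 365 days.
- Ratio: 365 / 15 = 24.3.

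**Illustration 2: period.** Assume days counted from treatment, screening at day 270, Year 1, 2 and 3 visits at days 365, 730 and 1095, and flares of 7 to 30 days each.

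*First flare early: starts on days 300, 800, 900 and 1000.*
- Per episode: 4 events, 1 in Screening to Year 1 and 3 in Year 2 to Year 3; flare days 4 × 7 = 28 to 4 × 30 = 120.
- One intermittent AE: 1 event in Screening to Year 1 and 0 in Year 2 to Year 3. With 7-day flares the last ends on day 1006, so 1006 − 300 + 1 = 707 days. With 30-day flares it ends on day 1029, so 1029 − 300 + 1 = 730 days. If ongoing at end of study, 1095 − 300 + 1 = 796 days.
- Ratio of listed duration to flare days, if resolved: 730 / 120 = 6.1 to 707 / 28 = about 25.

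*All flares late: starts on days 800, 900 and 1000.*
- Per episode: 3 events in Year 2 to Year 3; flare days 3 × 7 = 21 to 3 × 30 = 90.
- One intermittent AE: 1 event, still in Year 2 to Year 3; 1006 − 800 + 1 = 207 to 1029 − 800 + 1 = 230 days.
- Ratio: 230 / 90 = 2.6 to 207 / 21 = 9.9.

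The period therefore shifts only if the first episode fell in an earlier period. An imported AE behaves the same way: if later flares are treated as part of it, its only count is under the previous study. The ratios depend entirely on the assumed flare length and spacing.

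**What merging leaves unchanged.** The number of subjects with the event is 1 in every history above. The tables in SAP 11.7.1.1 to 11.7.1.3 count subjects, so their n (%) entries do not move. Duration is specified only for the AE listing (SAP 11.7.1.1), and SAP 11 describes no table by study period. The exposed outputs are m, the period flag and the listed duration.

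**The case against.** The strongest reply is that the documents, read together, support one record per exacerbation. Protocol 6.2 makes an exacerbation an AE of interest in its own right, 6.7 asks for collection of every event meeting that definition, and 6.6 lists onset and resolution dates among the data for an event. On that reading the waiver covers only waxing and waning within an event. This stands as a permissible reading, but 6.4 permits the opposite for anything an investigator calls intermittent, and no text settles which prevails. The rule on severity changes helps only in part: it dates changes of grade, does not clearly require symptom-free gaps to be dated, and is followed directly by the waiver.

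A reader might go further and infer that repeated late flares will collapse into one early, long event, and that the study thereby loses sight of delayed events. The documents do not support that:
- Merging depends on the investigator's characterization.
- The two categories cover new incidence as well as exacerbation, and the first onset of a new disorder is still dated and counted.
- Flares that are all late stay in the late period.
- An unexpected hospitalization is its own AE of interest, although a flare without admission has no such second route.

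Two further points on the other side stand. The study manual and CRF completion guidelines, which are not among the documents, may say how intermittent events are entered. Assessments are yearly and may be by telephone, so per-episode dates would rest partly on recall, and not dating every episode of a fluctuating condition can be a defensible choice. That favours allowing partial dates. It does not justify leaving the rule undefined for events that make up the primary endpoint.

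**Conclusion.** The point holds in a limited form. An undefined waiver, which in this study can reach only primary-endpoint events, allows recurrent flares to be recorded as one AE. SAP 10.6 then yields a lower event count, the period of the first episode, and a duration that includes symptom-free time, with no offsetting rule.

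The size cannot be estimated from the documents. The 24-fold ratio in Illustration 1 and the range of about 6 to 25 in the early-first-flare case of Illustration 2 show the mechanism under assumed flares; they are not expected effects. The conclusion rests on two conditions: that some subjects have recurrent flares, and that an investigator labels them intermittent. Subject-level incidence and worst-severity tables are unaffected. This is an inexpensive correction worth making, not a threat to the study's main safety conclusion.

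**What to change.** **Protocol 6.4.** Delete the waiver sentence, or limit it to symptom fluctuation within a single exacerbation. State that each discrete exacerbation that is an AE of interest or a related SAE is recorded as its own event with onset and resolution dates, partial dates being allowed. Since nothing else is collected, exempting these events amounts to removing the waiver in this study, and it is clearer to say so. A short description of what separates one exacerbation from the next would help sites apply the rule alike.

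**SAP 10.6.** Add that any event still recorded as intermittent, including one imported from the earlier study, is flagged in the listing and its duration labelled as a first-to-last span. Where a partial date prevents a duration from being calculated, leave it blank, in line with SAP 8.1.

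**Cost.** One or two protocol sentences, one SAP line and a few more CRF entries. Some dates will depend on recall between yearly contacts and will be approximate.

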6.5 Assessment of Causality

The Investigator's assessment of relationship of an AE to ADVM-043 is part of the documentation process, but it is not a factor in determining what is or is not reported. If there is any doubt as to whether a clinical observation is an AE, the event is to be reported.

Investigator should assess potential causes of each AE and events should be considered related if there is “a reasonable possibility of a causal relationship” rather than if “a causal relationship cannot be ruled out.” When assessing causality, Investigators should assess biological balancing — the probability that the suspect drug caused the AE must be weighed against the probability that an alternative candidate caused it.

Causality of AEs should be assessed in relation to ADVM-043, and not prior concomitant medications or study procedures in the previous treatment study. The relationship or association of ADVM-043 in causing or contributing to the AE is to be characterized using the following criteria:

- Definitely Related: A definite causal relationship exists between study drug administration and the AE; including a plausible time relationship to study drug administration, and it cannot be explained by underlying or concurrent disease or other drugs/exposures.
- Likely Related: There is a reasonable possibility that the study drug caused the AE; the event is unlikely attributed to underlying or concurrent disease or other drugs/exposures (i.e., alternative explanation). There is a reasonable time sequence to administration of the study drug.
- Unlikely Related: Underlying or concurrent disease or other drugs/exposures provide plausible alternative explanations. Temporal relationship to study drug administration makes a causal relationship improbable.
- Not Related: There is no association between the study drug and the reported event; there is a clear alternative explanation; a causal relationship is non-plausible.

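### Protocol 6.5 leaves no related category for an event with a reasonable possibility of causation, reasonable timing and a plausible alternative cause, so such events can be misclassified and some SAEs left uncollected

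*Protocol*

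**What the plan says.** Protocol 6.5 opens with a general rule: "Investigator should assess potential causes of each AE and events should be considered related if there is" "a reasonable possibility of a causal relationship". It rejects the looser standard under which an event is related whenever causation cannot be excluded, and it asks for balancing: "the probability that the suspect drug caused the AE must be weighed against the probability that an alternative candidate caused it".

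Four categories follow. Definitely Related allows no other explanation. Likely Related reads "There is a reasonable possibility that the study drug caused the AE; the event is unlikely attributed to underlying or concurrent disease" (the sentence goes on to cover other drugs and exposures) and adds a timing element: "There is a reasonable time sequence to administration of the study drug". Unlikely Related has two sentences: "Underlying or concurrent disease or other drugs/exposures provide plausible alternative explanations", and a second saying that the timing makes causation improbable. Not Related is for events with no association and a clear other cause.

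Three things depend on the rating:

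- **Collection.** Protocol 6.3: "Only SAEs related to ADVM-043 should be collected and reported".
- **Expedited reporting.** Protocol 6.8 applies the 24-hour report to related SAEs.
- **Analysis.** For this study, SAP 10.6 counts only Definitely and Likely as related. For events imported from the previous study the rule is different: "AE (External): includes Possibly, Probably and Definitely Related Adverse Events".

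AEs of interest are handled separately. Protocol 6.2 lists new malignancy, neurologic disorders, rheumatologic or other autoimmune disorders, and unexpected hospitalization. Protocol 6.7 has all of these collected, with no relatedness filter.

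**The concern.** The rule and the categories set different thresholds. The rule asks for a reasonable possibility after weighing; the lowest related category asks for that and for the alternative to be unlikely. The two differ when both causes remain credible after weighing.

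That situation is foreseeable here. Every subject has A1AT deficiency, and the protocol records augmentation therapy and exposure to mutagenic agents, so it expects competing explanations to arise. A new malignancy after a listed mutagenic exposure is one example. Protocol 1.0 says that effects may be delayed by months or years, so late onset alone need not make causation improbable.

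Relationship to ADVM-043 is part of the primary endpoint, and relatedness also defines which SAEs belong to it. A gap in the scale therefore affects how events in the primary endpoint are classified and, for some SAEs, whether there is a record to classify.

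**Working it through.** No arithmetic applies: the study is descriptive, the SAP gives no sample size justification, and the point concerns definitions. The check is to take one kind of event through the text. The event has a reasonable possibility of causation by ADVM-043, a reasonable time sequence and a plausible alternative cause.

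**Step 1: the general rule.** The event is related, unless the weighing favours the alternative so clearly that no reasonable possibility remains.

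**Step 2: the four categories.**

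| Category | What it requires | Does the event meet it? |
|---|---|---|
| Definitely Related | Definite causation; no other explanation | No: an alternative exists |
| Likely Related | Reasonable possibility; alternative unlikely; reasonable timing | No: first and third met, second not |
| Unlikely Related | Plausible alternative; timing makes causation improbable | No: first met, second not |
| Not Related | No association; clear alternative; causation not plausible | No |

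Read literally, no category fits. If the two sentences of Unlikely Related are taken as either/or, the event falls there and counts as unrelated.

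**Step 3: control cases.** With a reasonable possibility, reasonable timing and no plausible alternative, the rule says related and the category is Likely; the two agree. With no reasonable possibility, a plausible alternative and improbable timing, the rule says not related and the category is Unlikely or Not Related; again they agree. The mismatch is confined to the mixed case.

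**Step 4: what follows if the mixed-case event is rated unrelated.**

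| Type of event | Recorded? | What is lost |
|---|---|---|
| AE of interest, not serious | Yes (Protocol 6.2, 6.7) | Related flag (SAP 10.6); place in the related-AE summaries (SAP 11.7.1.1, 11.7.1.2) |
| AE of interest, serious | Yes, with seriousness noted (Protocol 6.6) | The same, plus the related-SAE summaries and the 24-hour report (Protocol 6.8) |
| SAE outside the list, such as a death without unexpected hospitalization or a disability outside the listed disorders | Not under Protocol 6.3 | The record itself; analysis cannot recover it |

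**Step 5: a second conflict.** Protocol 6.5 also states that the causality rating plays no part in deciding what gets reported. For SAEs outside the list, Protocol 6.3 makes it the deciding factor. Both statements cannot hold for those events.

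**The case against.** The strongest reply is that the balancing sentence already joins the rule to the categories: if the alternative loses the weighing, the event is Likely; if it wins and the timing is poor, the event is Unlikely. This does narrow the mismatch. An investigator who reads unlikely as merely less probable than the drug would place some mixed cases in Likely Related. It does not close the gap. When the two causes are about evenly balanced, causation can still be a reasonable possibility, yet the alternative is not unlikely. Weighing an alternative is a weaker condition than requiring it to be unlikely.

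A second reply is that an investigator facing the gap still has the express instruction to treat such an event as related, and Protocol 10.0 asks SAE reports to address reasonable possibility without mentioning alternatives. This stands in part. It means that an unrelated rating is a risk and not a certainty, and that different investigators may resolve the gap differently.

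Three stronger readings are tempting and are not supported:

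- **That any serious event of this kind goes uncollected.** AEs of interest, including unexpected hospitalization and new malignancy, are collected whatever the rating, and the SAP tabulates serious AEs of interest apart from related ones. Only SAEs outside the list are exposed.
- **That such events are necessarily rated Unlikely, giving a fixed bias toward no effect.** The event does not meet that definition in full either. What the text supports is inconsistent rating, with under-classification possible.
- **That the previous study's Possibly level was designed for this case.** SAP 10.6 gives only the labels; their definitions are not in the documents. It does show that imported and new events are flagged related on different scales.

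**Conclusion.** The point holds in this limited form. The categories in Protocol 6.5 do not carry out the section's own rule, and an event with a reasonable possibility, reasonable timing and a plausible alternative has no related category. For AEs of interest the possible loss is the related flag and, if serious, the 24-hour report. For SAEs outside the list it is the record itself.

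The size cannot be given. The documents contain no event counts, no share of events with competing causes and no information on how investigators would resolve the gap. Any percentage would only restate an assumption.

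The conclusion rests on taking the category wording at face value and on reading unlikely as a stricter condition than being outweighed. It is worth correcting because the rating feeds the primary endpoint and because an uncollected SAE cannot be restored at analysis.

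**What to change.** Bring the categories in Protocol 6.5 into line with its general rule, by one of two routes:

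1. Reword Likely Related so that a plausible alternative does not exclude it when a reasonable possibility remains after weighing. No new level is needed and SAP 10.6 can keep its present list.
2. Add a Possibly Related level for a reasonable possibility that coexists with a plausible alternative, and count it as related in Protocol 6.3, Protocol 6.8 and SAP 10.6, with the CRF updated to match.

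Neither route adopts the cannot-be-excluded standard that the protocol rejects, since both still require a reasonable possibility.

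Separately, reconcile the Protocol 6.5 statement that causality does not determine reporting with the Protocol 6.3 limit to related SAEs. Changing the categories alone leaves that conflict in place.

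The cost is a few lines in the protocol and, for the second route, one line in the SAP and a CRF change. The downside is slightly more events reported as related.
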